**Redoses:**

Up to three redoses of Bupivacaine .125% (10-15 mL) will be administered for inadequate pain control. The time to the first request for supplemental analgesia will be recorded on the study data sheet. The time, type and volume of bupivacaine used, and VAS scores before and 15 minutes after the re-doses will be recorded.

All other clinical management will be as per routine, and study participation will not interfere with anesthetic or obstetric care. Anesthesiologists will manage breakthrough pain in the usual manner (assessment of stage of labor and extend/density of neuraxial blockade, followed by the appropriate maneuver to reestablish adequate analgesia).

Following delivery, the patient will be asked to give one final VAS score and her overall satisfaction with labor using a 100 mm unmarked line (the left end labeled “not satisfied at all” and the right end labeled “extremely satisfied”). Mode of delivery, as well as the duration of the 1st and 2nd stage of labor, maximum oxytocin dose, maximum temperature recorded during labor, and any complaints for intrascapular pain will be recorded by study personnel.

Patient-Controlled Epidural Analgesia (PCEA) pump utilization data will be downloaded from epidural pumps after delivery. This will include the time to first PCEA request, the number of PCEA demands, the number of times that PCEA boluses were delivered, the total amount of local anesthetic consumed.

**DATA AND SPECIMEN BANKING: NA**

**DATA AND SPECIMEN MANAGEMENT:**

Group sample sizes of 91 in group 1 and 91 in group 2 achieve 80.276% power to detect a difference between the group proportions of 0.1250. The proportion in group 1 (the treatment group) is assumed to be 0.1250 under the null hypothesis and 0.2500 under the alternative hypothesis. The proportion in group 2 (the control group) is 0.1250. The test statistic used is

the two-sided Fisher's Exact Test. The significance level of the test is targeted at 0.0500. In order to account for drop-outs, we will recruit 110 patients per group.

Categorical data between groups will be compared using a chi-square or Fisher's exact test, and continuous data will be compared using a two-tailed t-test or Mann Whitney U test as appropriate. Time outcomes will be compared between groups using a Kaplan-Meier survival analysis technique with log rank test. Patients undergo a cesarean delivery or who do not request supplemental analgesia will be censored at the time of delivery. Labor pain will be calculated using the area under the VAS-time curve using the trapezium rule.

The subjects' identity will be guarded by assigning a numerical code, which is only known by the principal investigator. Data are stored in a department computer which is password protected. Each study subject will be assigned a study code number. The code will be used to link study data to patient identification (name) in a separate database. Subject data will be stored on secured computers at Northwestern University. Data access will be password-protected and only available to study investigators. The data forms will be de-identified after the chart review prior to analysis. 5 years after manuscript publication, both electronic and paper data will be destroyed using the current departmental standards.

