Epidural infusion pumps capable of delivering PIEB of local anesthetic with PCEA have become commercially available and many studies have attempted to assess the optimal parameter settings (including volume of programmed bolus, bolus interval, rate of bolus administration) to provide superior labor analgesia. Recently we completed a double-blinded randomized control trial evaluating two bolus delivery rates, hypothesizing that those patients randomized to receive higher bolus delivery rates would have improved labor analgesia. However, no difference was found between groups.(7) What is more, both groups had a mean cephalad sensory level to cold of T6. This sensory level is higher than the traditional goal of T10 (upper dermatome level of uterine innervation), but despite the adequate sensory level, a large number of patients required

supplemental physician-delivered boluses of local anesthetic during labor. Forty percent of the women in the high-rate group and 36% of the low-rate group required a manual re-dose during labor.(7) This suggests that either a higher volume, or higher concentration of local anesthetic (i.e., higher dose) is needed to maintain adequate labor analgesia.

Traditionally higher concentration local anesthetic solutions have been associated with increased motor blockade leading to a higher incidence of instrumental vaginal delivery.(8) Several local anesthetic solutions with varying drug concentrations are available for labor analgesia and are used clinically in the United States. We plan to perform a randomized, controlled, double-blind study to test the hypothesis that patients whose labor analgesia is maintained using PIEB with low-volume bolus (6.25 mL) of a higher local anesthetic concentration solution (0.1% bupivacaine with fentanyl 2.0 mcg/mL) will require less supplemental analgesia (manual provider re-doses) than patients whose PIEB is delivered with a high-volume bolus (10 mL) of lower density local anesthetic solution (0.0625% bupivacaine with fentanyl 2.0 mcg/mL).

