## **STUDY-WIDE NUMBER OF PARTICIPANTS:**

In a previous study in which 10 mL of a bupivacaine/fentanyl mixture was injected at 300 mL/h and 100 mL/hr, the duration to the first request for supplemental analgesia (manual bolus) was 356 minutes and 301 minutes with a 36% and 40% re-dose rate respectively.(7) We hypothesize that the group with low-volume bolus (6.25 mL) of greater density solution (0.1% bupivacaine with fentanyl 2.0 mcg/mL) will have fewer patients requiring supplemental analgesia than patients whose PIEB is delivered with a high-volume bolus (10 mL) of lower density local anesthetic (0.0625% bupivacaine with fentanyl 2.0 mcg/mL).

Assuming a 20% reduction in re-dose from 40% to 20%, a power of 0.8, and an alpha of 0.05, we estimate that we will need 91 patients per group. In order to account for drop-outs, we will recruit 110 patients per group.

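### The power stated in the analysis section (80.276% at 91 per group for 12.5% vs 25%) is really 51.5%, and its assumptions contradict the 40% to 20% plan

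*Combined protocol and SAP*

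**What the plan says.** The combined protocol and SAP justifies 91 analysed and 110 recruited per group twice, on different assumptions.

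- **Study-Wide Number of Participants** sets the target as follows: "Assuming a 20% reduction in re-dose from 40% to 20%, a power of 0.8, and an alpha of 0.05". It expects fewer re-doses in the low-volume, high-concentration group.
- **Data and Specimen Management** says that group sizes of "91 in group 1 and 91 in group 2 achieve 80.276% power to detect a difference between the group proportions of 0.1250". The treatment proportion "is assumed to be 0.1250 under the null hypothesis and 0.2500 under the alternative hypothesis". For the comparator: "The proportion in group 2 (the control group) is 0.1250". The test is "the two-sided Fisher's Exact Test" at a significance level of 0.05.

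Both refer to a two-group comparison of proportions, and the primary outcome under Study Endpoints is binary (need for a physician-delivered bolus). The Background reports the previous study's rates: "Forty percent of the women in the high-rate group and 36% of the low-rate group required a manual re-dose during labor". Study-Wide Number of Participants cites the same study but attaches 36% to the 300 mL/h arm and 40% to the 100 mL/h arm, the opposite way round.

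**The concern.** The same 91 per group cannot give about 80% power both for 40% vs 20% and for 25% vs 12.5%. The second difference is much smaller, and the lower baseline does not make up for that. One of the two statements had to be wrong.

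The analysis-section paragraph also fits the rest of the protocol badly. Its control rate of 12.5% is about a third of the 36% to 40% seen in the previous study. It gives the treatment group the higher proportion, although the hypothesis expects the low-volume, high-concentration group to need fewer re-doses.

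This is the only place where power is tied to a named test. If it is taken at face value, a non-significant result could be reported as coming from a trial with 80% power to find a 12.5-point difference. The protocol would also carry two incompatible target effects, so a reader could not tell which one the trial was designed to detect.

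**Working it through.** **Inputs, all from Data and Specimen Management:** n = 91 per group, proportions 0.25 and 0.125, two-sided Fisher's exact test, alpha 0.05. Nothing from outside the document is needed.

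**Method.** For each pair of counts (x, y), compute the two-sided Fisher p-value and sum the binomial probabilities of the pairs that reject:

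Power = Σ Bin(x; n, p₁) · Bin(y; n, p₂) over all (x, y) with Fisher p ≤ 0.05.

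Defining the two-sided p-value by minimum likelihood or by doubling the smaller tail gives the same power.

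**Step 1: try to reproduce 80.276% at 91 per group.** It does not reproduce by any method tried.

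| Method, 0.25 vs 0.125, n = 91 | Power |
|---|---|
| Fisher, two-sided (as stated) | 51.5% |
| z with continuity correction | 50.4% |
| z, pooled variance | 58.0% |
| Uncorrected chi-square, exact enumeration | 58.4% |
| z, unpooled, or arcsine | 59.0% |
| Fisher, one-sided | 64.1% |
| z, pooled, one-sided | 69.9% |

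The shortfall for the stated test is 80.276 − 51.518 = 28.8 percentage points.

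**Step 2: find the n that gives the printed figure.** Same proportions, two-sided Fisher:

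| n per group | Power |
|---|---|
| 91 | 51.518% |
| 110 | 60.804% |
| 164 | 79.976% |
| 165 | 80.276% |

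The printed value appears exactly at 165, the first n at which power reaches 80%.

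**Step 3: check the other justification, 40% vs 20%.** Without continuity correction, with p̄ = 0.30 and d = 0.20:

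n = [1.960·√(2·0.30·0.70) + 0.842·√(0.40·0.60 + 0.20·0.80)]² / 0.20² = 81.2.

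With continuity correction:

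n' = (n/4)·[1 + √(1 + 4/(n·d))]² = (81.2/4)·[1 + √(1 + 4/16.24)]² = 90.9, rounded up to 91.

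Exact Fisher power at 91 per group is 80.8%. Study-Wide Number of Participants is therefore correct on its own terms.

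**Step 4: sensitivity to the control rate.** The two sections disagree about which arm of the previous study had 36% and which had 40%. Fisher power at 91 per group with a 36% control rate:

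| Comparison | Effect kept from the plan | Power |
|---|---|---|
| 36% vs 16% | 20-point difference | 84.3% |
| 36% vs 18% | halving of the rate | 74.3% |
| 36% vs 20% | 20% rate in the treatment arm | 62.2% |

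The lower control rate reduces power only if the effect in percentage points shrinks with it.

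**The case against.** The strongest defence is that the sample size is right. The section headed as the sample-size justification supports 91 per group, so enrolment, endpoint and analysis are unaffected if that section governs. This is correct, and it limits the fault to the stated power and its assumptions.

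Four narrower points also have some force.

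- **Direction.** The paragraph does not say which regimen is the treatment group. If it were the high-volume arm, the direction would agree with the hypothesis. The natural reading is that the 10 mL bolus, used in the previous study, is the control, which makes the direction reversed. This is a likely reading, not a proven one, and two-sided power with equal groups does not depend on it.
- **Test.** The same section later allows either chi-square or Fisher's test for categorical data. Uncorrected chi-square raises the power only to 58.4% at 91 per group and 66.9% at 110.
- **Origin.** That the proportions and power were carried over from a 165-per-group calculation is inferred from the exact match. The document does not say so.
- **Control rate.** The 36% scenarios with lower power also use a smaller absolute effect. With the full 20 points kept, power rises to 84.3%. The swapped 36% and 40% is a real inconsistency but a secondary one.

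None of these rescues the 80.276%, and no other section corrects it.

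**Conclusion.** The concern holds: the power statement is wrong as written. For 12.5% vs 25% with a two-sided Fisher's exact test at 0.05, power is 51.5% at 91 per group. The 60.8% at 110 is an upper bound, because it assumes that no one drops out. Reaching 80% takes 165 analysed per group. The result rests only on the paragraph's own inputs, and no alternative method tried exceeds 69.9%.

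The paragraph is also incompatible with the 40% to 20% target, for which 91 per group gives 80.8%. The error lies in the analysis-section power claim, and nothing here shows that 91 is too few for 40% vs 20%.

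**What to change.** Replace the power paragraph in Data and Specimen Management with one consistent with Study-Wide Number of Participants, for example:

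> With 91 patients analysed per group, a two-sided Fisher's exact test at the 0.05 level has 80.8% power to detect a reduction in the proportion needing a manual re-dose from 40% (high-volume, low-concentration) to 20% (low-volume, high-concentration).

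Name the regimens, as here, so that the direction is explicit. If a 12.5-point difference is also of interest, state its power for 12.5% vs 25%: 51.5% at 91 per group, and at most 60.8% at 110. Reconcile which arm of the previous study had 36% and which had 40%, and quote power at a 36% control rate with the assumed effect spelled out (84.3% for 36% vs 16%, 74.3% for 36% vs 18%, 62.2% for 36% vs 20%).

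**Cost.** If 40% to 20% is the intended target, this is wording only and needs no extra patients. If the sponsor instead wants 80% power for 12.5% vs 25%, it needs 165 analysed per group. With the loss allowance already in the plan (91 of 110), that means recruiting 165 × 110/91 = 199.5, or 200 per group.

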## **OBJECTIVES:**

Aim: To evaluate the association between bolus volume and concentration of local anesthetic during maintenance of labor analgesia with programmed intermittent epidural bolus (PIEB) analgesia.

Hypothesis: Patients whose labor analgesia is maintained using PIEB with low-volume bolus (6.25 mL) of higher local anesthetic concentration solution (0.1% bupivacaine with fentanyl 2.0 mcg/mL) will have a longer duration of adequate analgesia (time to first manual re-dose request) than patients whose PIEB is delivered with a high-volume bolus (10 mL) of lower concentration local anesthetic solution (0.0625% bupivacaine with fentanyl 2.0 mcg/mL).

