### **STUDY ENDPOINTS:**

**Primary outcome:** Need for supplemental physician-delivered bolus of local anesthetic.

**Secondary outcomes:** Time to first request for supplemental analgesia, total hourly bupivacaine consumption, mode of delivery, and motor block throughout labor and at 10 cm cervical dilation, sensory level throughout labor and at 10 cm cervical dilation, pain burden as defined as area under the pain-time curve, patient satisfaction.

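### The censoring rule, as worded, turns a recorded first request into a censored time whenever the woman later has a cesarean

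*Combined protocol and SAP*

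**What the plan says.** All references are to the combined protocol and SAP.

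- **Method** (Data and Specimen Management): "Time outcomes will be compared between groups using a Kaplan-Meier survival analysis technique with log rank test".
- **Censoring** (next sentence, same section): "Patients undergo a cesarean delivery or who do not request supplemental analgesia will be censored at the time of delivery". This is the only censoring rule in the documents.
- **Outcome** (Study Endpoints): the first-listed secondary outcome is "Time to first request for supplemental analgesia". The hypothesis under Objectives is framed on the same quantity, and predicts a longer time in the low-volume, higher-concentration group.
- **Data** (Redoses): "The time to the first request for supplemental analgesia will be recorded on the study data sheet". No exception is made for women who later deliver by cesarean. Mode of delivery is recorded afterwards.

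**The concern.** The rule has two triggers joined by *or*: cesarean delivery, and absence of a request. Nothing confines the first trigger to women who have not yet asked for supplemental analgesia. Applied as written, a woman re-dosed at 3 hours whose cesarean takes place at 10 hours enters the analysis as event-free for 10 hours.

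That uses something that happens later (mode of delivery) to erase an event already observed, and keeps the woman in the risk set after her event. The Kaplan-Meier curve for duration of adequate analgesia is pushed upward, events are lost, and the contrast between arms is diluted. Mode of delivery is itself a secondary outcome, so equal cesarean shares in the two arms cannot simply be assumed. Two analysts could also read the sentence differently and draw different curves from the same data.

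**Working it through.** **Step 1. Case logic (needs no figures).**

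| Delivery | Earlier request | Without the cesarean condition | Rule as written |
|---|---|---|---|
| Vaginal | No | Censored at delivery | Same |
| Cesarean | No | Censored at delivery | Same |
| Vaginal | Yes | Event at request | Same |
| Cesarean | Yes | Event at request | Censored at delivery |

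Only the last row changes, always from event to non-event and always to a longer time.

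**Step 2. Inputs.** From the documents: 91 per group and 40% versus 20% re-dosed (Study-Wide Number of Participants); women who deliver or need a re-dose within 90 minutes are excluded (Exclusion criteria). Assumed, because the documents do not give them: cesarean share c of 10%, 20% or 30%, labor length, and a constant request hazard after 90 minutes.

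The plan's 91 per group reproduces for 40% versus 20%:
- uncorrected n = [1.96·√(2·0.3·0.7) + 0.842·√(0.4·0.6 + 0.2·0.8)]² / 0.2² ≈ 81.2, that is 82;
- with continuity correction, (81.2/4)·[1 + √(1 + 4/(81.2·0.2))]² ≈ 90.9, that is 91.

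**Step 3. Events.** Expected requests = 91·0.40 + 91·0.20 = 54.6. If a share c of requesters later has a cesarean, 54.6·(1 − c) events remain: 49.1, 43.7 and 38.2 for c = 10%, 20% and 30%.

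**Step 4. Kaplan-Meier curve.** If cesarean is unrelated to request time and labor length, the literal rule treats a fraction c as never requesting, so the curve estimates 1 − (1 − c)(1 − S(t)) instead of S(t). With S = 0.615 at 8 hours in the control arm (simulated) and c = 20%: 1 − 0.8·0.385 = 0.692. Simulation gave 0.652, 0.692 and 0.731 for the three shares. In the treatment arm, 0.819 becomes 0.837, 0.855 and 0.873.

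**Step 5. Log-rank power (simulated, 91 per arm, two-sided 5%).** Model A has lognormal labor (median 480 minutes, log-SD 0.5), 5,000 trials per scenario. Model B has delivery at 90 minutes plus a gamma time (shape 4, scale 100 minutes) and a hazard ratio of ln 0.8 / ln 0.6 = 0.437, 3,000 trials per scenario.

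| Cesarean share | A: events kept | A: literal | B: events kept | B: literal |
|---|---|---|---|---|
| 10% | 88.5% | 83.2% | 85.2% | 78.9% |
| 20% | 89.2% | 77.0% | 85.1% | 71.8% |
| 30% | 88.3% | 67.8% | 85.0% | 63.7% |

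Fewer events alone do not explain the fall. The Schoenfeld formula at a hazard ratio of 0.437 gives 86.4% with 54.6 events and 82.7%, 78.1% and 72.6% after the losses in Step 3. The rest comes from women who stay in the risk set after their request, which pulls the hazard ratio toward 1.

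If requesters have twice the odds of cesarean (20% in non-requesters), model B falls from 85.0% to 61.1%.

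**Step 6. Type I error (model A, 40% in both arms, literal rule).** 4.6-5.2% with equal cesarean shares. With 20% versus 30% it is 9.2%, against 4.9% when events are kept. With 20% versus 25% it is about 5-6%.

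**The case against.** The best defense is that Kaplan-Meier practice settles the matter. A woman leaves the risk set at her first request, so there is no later time at which to censor her. Read this way, the sentence means that women who reach delivery by either route without the event are censored there, and the cesarean words are merely redundant. Many analysts would do this, and the grammar of the sentence is visibly damaged.

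A second defense is that the rule is shared by several time variables. The Redoses section also records "Mode of delivery, as well as the duration of the 1st and 2nd stage of labor", together with time to first PCEA request. Censoring cesarean patients at delivery is ordinary for stage-of-labor durations. However, stage durations are not listed under Study Endpoints, and nothing assigns the cesarean condition to them.

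Both readings are plausible, but neither is written down. Under either one, the wording proposed below for time to first request does no harm.

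The limits on the consequence stand. The outcome is secondary, the binary primary is untouched, and the plan sets no power target for the log-rank test. The power figures rest on assumptions. The power statement in Data and Specimen Management uses 12.5% and 25% instead of 20% and 40%; on those rates, model A gives only about 61% power with events kept and about 51% under the literal rule at a 20% cesarean share. The 9% type I error needs a 10-point cesarean imbalance that the documents do not suggest, so it should carry little weight.

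**Conclusion.** The point holds. For time to first request, the cesarean condition can only remove observed events. That follows from the wording and depends on no assumed figure.

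The proportion of events lost equals the share of requesters who later have a cesarean. At assumed shares of 10-30% that is about 5 to 16 of 55 events. The power loss is about 5 to 21 percentage points across the two labor models if cesarean is unrelated to requesting, and larger if requesters are more likely to have a cesarean. Type I error stays near 5% when cesarean shares are equal between arms.

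This should be corrected before analysis. It does not threaten the primary comparison.

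**What to change.** In Data and Specimen Management, replace the censoring sentence, for this outcome, with:

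> For time to first request, the event is the first request for supplemental analgesia at its recorded time, whatever the later mode of delivery. Only patients with no request are censored, at the time of delivery.

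If the cesarean condition was meant for a different time outcome, name that outcome and give its censoring rule separately.

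The cost is one sentence. Request time and mode of delivery are already collected, and neither the sample size nor any clinical procedure changes.

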### **PROVISIONS TO MONITOR THE DATA TO ENSURE THE SAFETY OF PARTICIPANTS:**

A data monitoring committee consisting of the Department of Anesthesiology Director of Research, a statistician and a faculty member from the obstetrics department along with the study research personnel will periodically evaluate the data collected to determine whether participants remain safe. Safety data and adverse event data will be reviewed using the medical record and data collection form. It will be reviewed every 110 subjects or if one of the study subject experiences a rapid response team intervention and review. Data will be compared between groups using the chi2 statistic or the Fisher's exact test. A  $P < 0.05$  will be required to reject the null hypothesis.

### **WITHDRAWAL OF PARTICIPANTS:**

If the subject wishes to withdraw from the study during the hospitalization she will need to contact a study team member who will then contact the PI by secured-email to inform her about the event that led to early study termination.

